### **I. BACKGROUND AND SIGNIFICANCE**

#### **Acute orthopedic musculoskeletal injuries are prevalent and costly.**

Acute musculoskeletal orthopedic injuries (e.g., fractures, dislocations, also known as traumatic musculoskeletal injuries) represent the leading cause of adult hospital admissions. Approximately 20-50% of patients go on to develop persistent (e.g., chronic) pain and disability despite making adequate recovery of their bones and soft tissues. These patients tend to continue to have multiple surgeries and medical appointments, resulting in increased health care costs and a significant public health burden.

#### **Psychosocial factors in the acute phase after the orthopedic injury, predict chronic pain and disability.**

Catastrophic thinking about pain, pain anxiety, depression, and prolonged opioid use are established risk factors for disability and pain in patients with musculoskeletal injuries, regardless of the severity, location or type of injury. Recognizing these psychosocial factors early in the recovery process creates a window of opportunity to identify and intervene with patients who are at risk for chronic pain and disability in the acute phase, when psychosocial treatments are most effective. A recent systematic review conducted by our team showed that there is no evidence based psychosocial treatments targeting psychosocial factors in patients with acute orthopedic injuries. This provides urgency for the development of feasible, accepted, evidence-based interventions to prevent chronic pain and disability in at risk patients with orthopedic musculoskeletal injuries early in the recovery process, along with medical care.

#### **The care of patients with orthopedic musculoskeletal injuries follows an outdated biomedical model.**

Current usual care for patients with acute traumatic musculoskeletal injuries consists primarily of surgical interventions and pain medications. However, medical care is undergoing a shift in priorities recognizing the multifactorial influences on successful recovery after injury, and the pivotal role of psychosocial factors within orthopedic care. Although surgeons are now aware of the importance of psychosocial factors in recovery after musculoskeletal injuries, they are often uncomfortable referring patients for outpatient care. Referrals are often done after multiple unsuccessful medical procedures, when patients have become invested in a medical cure, pain has already become chronic, and treatments are generally less efficacious.

Further, engaging pain patients in traditional mental health treatments has been challenging due to stigma associated with mental health concerns among this population. Referrals are also challenging due to lack of trained providers, particularly for patients in rural areas for whom travel to clinic for additional visits would be an additional burden. Travel to clinic is a burden even for patients who are geographically proximal to clinic but are often unable to drive and have to rely on family and friends for transportation.

### **Mind body approaches delivered to patients with acute orthopedic injuries may help.**

Over the last decade, mind-body interventions have demonstrated utility for improving psychological and pain-related outcomes and have potential to help patients who seek care for musculoskeletal injuries in orthopedic surgical practices as an adjunct to medical care. Brief mind body programs show promise among orthopedic patients. In a fully powered randomized controlled single blinded study we have shown that a 60-seconds, personalized, live video mindfulness exercise is highly accepted, feasible and useful for patients with non-traumatic hand and upper extremity orthopedic conditions waiting for their medical appointment with a surgeon, and is associated with momentary decrease in pain and distress compared to an attention placebo control.

We developed the first mind-body program – The Toolkit for Optimal Recovery after orthopedic injury (TOR) – to prevent chronic pain and disability in at-risk patients with orthopedic injuries. We used the fear avoidance model as the theoretical framework to guide the development of TOR. The fear avoidance model provides a useful framework to understand the transition from acute to persistent or chronic symptoms in patients with acute orthopedic injuries. The model specifies that catastrophic thinking about pain (i.e., misattributions about pain), and anxiety about pain (i.e., hypervigilance to pain sensations) lead to avoidance of activity and escape behaviors, which in turn, lead to increased pain and disability. Using this model and feedback from surgeons and patients with acute orthopedic injuries, we iteratively developed a 4-session, individual, live video mind-body program, TOR, focused on optimizing recovery and preventing chronic pain and disability in patients with orthopedic injuries who endorse catastrophic thinking about pain and/or pain anxiety and are thus at risk for chronic pain and disability, based on our prior work.

TOR directly targets catastrophic thinking about pain (i.e., misconceptions about pain and activity, hopelessness, helplessness and magnification of pain) and pain anxiety (i.e., cognitive, physiological and pain avoidance elements) through teaching relaxation response and mindfulness skills, correction of misconceptions (e.g., through education and adaptive thinking techniques), acceptance and value-based engagement in activities, and activity pacing. The goal is to “confront” rather than “avoid” the pain experienced and activities that may be associated with pain and thus prevent the transition toward chronic pain. Each TOR session is about 45 minutes, and all 4 are delivered within a period of 4-5 weeks (TOR and control arm will be yoked for the timing of interventions). Brief mind-body interventions have shown to be feasible to implement and acceptable to patients in busy orthopedic practices. The live video delivery format aims to bypass established barriers to biopsychosocial care for orthopedic patients (e.g., transportation, inflexible schedules). These format/dosage considerations are all in line with feedback we received from surgeons and patients with acute orthopedic injuries during the iterative treatment development process. It is unlikely that TOR intervention causes any risk of physical or psychological harm other than potential experience of psychological discomfort while discussing their experiences during intervention sessions. As indicated, our pilot feasibility RCT of TOR at MGH showed evidence for feasibility, acceptability, and satisfaction for TOR.

## II. SPECIFIC AIMS

**Aim 1 (Year 1): Develop a semi-structured qualitative interview script that will be used to conduct separate focus groups with surgeons and with supportive medical staff (e.g., nurses, medical assistants) at the 3 original sites.**

**Deliverables:** 1) Develop a study protocol including milestones, and strategies to maximize success of Aim 2; 2) develop education materials to facilitate referrals and study procedures for surgeons and staff; and 3) finalize the Toolkit for Optimal Recovery after Orthopedic (TOR), as needed; 4) anticipate and develop alternative plans for potential study challenges, at each site.

**Aim 2 (Years 2, 3, & 4): Conduct a 4-site feasibility RCT (180 participants total, 60 at the parent site, 50 completers; 40 per child site; 33-34 completers per site) to compare the TOR versus a minimally enhanced usual care control (MEUC). The trial will be informed by our preliminary data and activities of Aim 1. This trial will be used to 1) determine whether the study methodology and TOR meet a priori set benchmarks necessary for the success of a subsequent efficacy trial and 2) determine whether the study methodology and TOR meet a priori set benchmarks for the 27 secondary outcomes related to the success of the subsequent efficacy trial. After the conclusion of the intervention, we will also solicit feedback from orthopedic trauma providers about their perceptions of the feasibility, acceptability, and appropriateness of the TOR study in their clinic.**

**Deliverables:** 1) refined protocol of patient recruitment, study protocol, and fidelity materials, 2) study procedures that are individualized to each site and feasible, appropriate, and accepted by patients and staff, and have the potential to decrease pain and increase physical function/decrease disability; 3) ability to meet feasibility, acceptability, appropriateness and fidelity benchmarks at each of the 4 sites in preparation for the UG3/UH3.

The PI has experience adapting and conducting mind body interventions via videoconferencing, and has received IRB approval on 2 ongoing studies assessing efficacy of mind body interventions via videoconferencing that are currently progressing.

## III. SUBJECT SELECTION

All adult, English-speaking, 18 or older patients presenting to the each of the 3 Level 1 Trauma Centers sites with a traumatic musculoskeletal injury will be invited to enroll. The study will be described in detail and a member of the IRB-approved study staff trained in obtaining consent will obtain informed consent. Patients will be given a copy of the consent form and be informed that their participation is voluntary and that they can withdraw at any time. Subjects will be identified by referrals through surgeons and other orthopedic medical providers. We will aim at

recruiting N = 60 participants at the parent site and N = 40 participants per child site (total N = 180).

### **Aim 1: Inclusion/Exclusion Criteria**

Eligible participants must meet the following inclusion criteria:

- 1) Male and female medical staff (surgeon, fellow, resident, nurse, medical assistant, front desk, phone, research staff) in the Level 1 Trauma Center of one of the 3 sites.
- 2) Willingness to participate

One or more of the following exclusion criteria will render a participant ineligible:

- 1) Chief of orthopedic trauma

### **Aim 2: Inclusion/Exclusion Criteria**

Eligible patients must meet the following inclusion criteria:

- 1) Outpatient adults in the Level 1 Trauma Center at the 4 sites
- 2) Age 18 or older
- 3) Able to meaningfully participate (English fluency and literacy, stable living situation as determined by the medical staff at each site).
- 4) A score of 8/10 or more on the Short Portable Mental Status Questionnaire ONLY IF a participant is 65 or older, or if a participant's cognitive abilities are unclear to research staff
- 5) Sustained one or more acute orthopedic injuries (e.g., fracture, dislocation, rupture) approximately 1-2 months earlier (acute phase).
- 6) PCS  $\geq$ 20 or PASS-20  $\geq$ 40
- 7) Willingness to comply with the study protocol, including randomization, questionnaire completion, and potential home practice and weekly sessions.
- 8) No psychotropics for at least 2 weeks prior to initiation of treatment or stable for >6 weeks and willing to maintain a stable dose
- 9) Cleared by orthopedic surgeon for activities using the injured limb within the next 4 weeks

One or more of the following exclusion criteria will render a patient ineligible:

- 1) Serious comorbidity expected to worsen in the next 6 months (e.g., malignancy)
- 2) Current untreated or unstable severe mental health conditions like bipolar disorder, schizophrenia, or active substance use
- 3) Current suicidal ideation
- 4) Other unmanaged serious non-orthopedic injuries that occurred alongside the orthopedic injury (i.e., TBI, ruptured internal organs, etc.)
- 5) Currently in litigation or under Workman's Comp
- 6) Surgery complications (e.g., uncontrolled infection, need for repeat surgery)
- 7) Self-reported pregnancy
- 8) Practice of meditation, or other mind body techniques that elicit the RR, for at least 45 total min a week each week over the last 3 months

After the conclusion of the RCT, we will also solicit feedback from orthopedic trauma providers (up to 80 participants total) about their perceptions of the feasibility, acceptability, and appropriateness of the TOR study in their clinic.

Eligible participants must meet the following inclusion criteria:

- 1) Male and female medical staff (surgeon, fellow, resident, nurse, medical assistant, front desk, phone, research staff) in the Level 1 Trauma Center of one of the 4 sites.
- 2) Willingness to participate

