## Recruitment

**Aim 1:** Participants will be surgeons and medical staff at each of the 4 sites. We will conduct separate focus groups with surgeons and with the rest of the medical staff. Trauma chiefs (Co-Is on this grant) will not be included in the focus groups to avoid bias. The site PI and surgeon champion at each site, with support from the trauma chiefs will give presentations during the staff meetings to discuss the aim of the study, present preliminary data, discuss potential benefits to patients, and encourage participation. The RA at each site will next assist with recruitment, consent, and scheduling focus groups.

**Aim 2:** Participants will be recruited from each of the 4 Level 1 Trauma Center sites: MGH, Kentucky, Dell and Vanderbilt following a recruitment protocol developed and individualized for each site, consistent with prior recommendations, and informed by aim 1. Potential participants will be identified through screening of the medical record by the RA (injury in the prior 1-2 months, consistent with our preliminary data). The RA will next notify the medical staff (medical assistant) who will alert the surgeons. The surgeon will do a “warm hand-off” and introduce the RA and the study to the participants at the end of the medical visit. The RA will assess for eligibility (per criteria above). All participants will sign a consent form in REDCap prior to study procedures. All forms of recruitment will be submitted for IBR approval prior to use. Participants who meet eligibility criteria will complete baseline questionnaires on an iPad or on paper in clinic. The RA will be available to answer any questions.

Eligible cases may also be identified by daily screening of Epic admission reports.

After the conclusion of the intervention, we will also solicit feedback from orthopedic trauma providers about their perceptions of the feasibility, acceptability, and appropriateness of the TOR study in their clinic. Participants will be surgeons and medical staff at each of the 4 sites. Site PIs and surgeon champions will distribute survey links via email to providers at their site. After reviewing a consent fact sheet, participants will be asked to complete a brief demographic questionnaire as well as a brief survey regarding their perceptions on the implementation of the TOR study in their clinic (11 items).

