
For the provider feedback surveys, surgeons and medical staff at each of the 4 sites will be asked to participate. Up to 80 providers are expected to participate. Medical professionals who choose to participate will provide implied consent based on their review of a study fact sheet in REDCap. All potential participants will be provided with a study fact sheet as the first page of a REDCap survey. The study fact sheet provides detailed information on the methodology and purpose of the study and the potential benefits/ risks associated with participating. All participants will be ensured that participation is strictly voluntary and confidential. In addition, the study fact sheet will inform the participants about the confidentiality measures that the research group will take during the process. Only members of the research team will have access to the data, and data will be de-identified as to not contain identifiable or confidential information. The study fact sheet will include pertinent information on study design, risks and benefits, and voluntary nature of the research and confidentiality. Participants will be encouraged to review the study fact sheet in its entirety before continuing to complete the brief REDCap survey. The study fact sheet will also contain the names and numbers of members of study staff that participants can contact if they have additional questions

or concerns. Due to the nature of this study and the minimum risk, we would like to waive the written documentation of informed consent. The consent process will be executed in a manner consistent with the IRB approved protocol, and the most recent version of the IRB-approved protocol will be used.

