Participants randomized to TOR will undergo set-up for the live video intervention prior to leaving the clinic. This includes: 1) installing Zoom and teaching participants how to use it; 2) scheduling their 4 weekly intervention sessions with the clinician; 3) setting up EZ texting to receive reminders; and 4) installing the TOR web platform (with session content and guided exercises) as an app on their phones. Participants who do not own a smart phone will be given one, and the RA will set their phone up at the first visit. We will also provide study participants with a data plan for the duration of the study, or brainstorm ways to access free internet (e.g., library, friends' houses), if needed. Our study team has used these strategies in prior studies. The RA will also schedule the participant's first session of TOR and ensure the participant writes down the date and time of the first session.

In order to ensure that participants in the TOR program are familiar with Zoom, the psychologist will schedule a brief session to go over how the software works and prepare the participants for the intervention.

Participants randomized to TOR will also receive daily text reminders through Twilio to practice program skills as well as record their skills practice if they consent to receive text reminders.

For the provider feedback surveys, surgeons and medical staff at each of the 4 sites will be asked to participate. Up to 80 providers are expected to participate. Participants will provide implied informed consent prior to participation. After reviewing a consent fact sheet, participants will be asked to complete a brief demographic questionnaire as well as a brief survey regarding their perceptions on the implementation of the TOR study in their clinic (11 items). Site PIs and surgeon champions will distribute surveys to providers at their site. We have the full support from the orthopedic leadership at each site for these activities.

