## **IX. MONITORING AND QUALITY ASSURANCE**

Electronic information will be stored in REDCap (Research Electronic Data Capture), a free, secure, and HIPAA-compliant web-based application hosted by the Partners HealthCare Research Computing Enterprise Research Infrastructure & Services (ERIS) group (based at the PHS Needham corporate datacenter). Data will be stored on password protected computers that will be stored in secure locations at all times. Paper data files (with coded subject identification) will be stored in a locked filing cabinet. Only research staff will have access to these data locations.

A unique anonymous identifier will be assigned to each subject; subsequently, all data collected will be associated exclusively with this identifier. This includes all questionnaires administered over the course of the study, as well as home practice logs.

Data from this study will be stored for three years after the publication of all study results, at which time all paper data files will be shredded, and computer files will be deleted.

The following study staff will be blinded: 1) overall PI; 2) site PIs; 3) surgeon champions; 4) study statistician; 5) RA involved with any post and follow up self-report and objective assessments; 6) statistician who is performing blinded analyses.

To achieve RA blindness, treatment assignment will be done by randomization RA, who will not be directly involved in evaluation or data collection. Survey data collection will be conducted by another RA who will be blinded to participant treatment assignment. Participant self-report surveys will be implemented using secured online survey software, which will significantly limit the potential of the RA to introduce bias. The overall PI, site PIs and surgeon champions will not be involved in the group assignment or collection of data. Also analyses will be conducted when data are unlocked. The study statistician and statistician who perform blinding analysis will not have access to randomization algorithm key.

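### The provider survey does not exclude study-affiliated staff or record study role, so its ratings of the trial are at risk of upward bias of unknown size

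*Combined protocol and SAP*

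**What the plan says.** **Who may answer.** Section III (Aim 2: Inclusion/Exclusion Criteria) ends with the criteria for the post-trial provider survey. The eligible list of medical staff runs from surgeons to "medical assistant, front desk, phone, research staff) in the Level 1 Trauma Center of one of the 4 sites". The only other criterion is willingness to take part. No exclusion is listed.

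**What they rate.** Providers are asked "about their perceptions of the feasibility, acceptability, and appropriateness of the TOR study in their clinic". The instrument has 11 items. No scale, scoring rule or pass mark is given for it.

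**How many.** Section IV: "Up to 80 providers are expected to participate". This is a ceiling, with no response-rate or precision target.

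**Who sends it.** Recruitment, Aim 2: "Site PIs and surgeon champions will distribute survey links via email to providers at their site". Section V repeats this: "Site PIs and surgeon champions will distribute surveys to providers at their site". Section IX counts both roles as study personnel: "The following study staff will be blinded: 1) overall PI; 2) site PIs; 3) surgeon champions".

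**The Aim 1 comparison.** The Aim 1 criteria have one exclusion, "Chief of orthopedic trauma". The Recruitment section gives the reason: "Trauma chiefs (Co-Is on this grant) will not be included in the focus groups to avoid bias". Section V repeats it.

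**Safeguards.** Section IV says that taking part in the survey is voluntary and confidential, with responses entered in REDCap and de-identified, though the research team can see the data.

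**Analysis.** Section VI (Aim 2) promises descriptive statistics. It does not mention the provider survey or any breakdown by study role.

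**The concern.** The survey asks respondents to judge the study itself. A co-investigator, site PI, surgeon champion or research assistant on the trial has a stake in a favourable answer. The protocol accepts that reasoning for one of these groups in Aim 1, but the survey criteria do not repeat the rule and do not say why. Without a question on study role, a reader of the pooled result could not tell how much of it came from people who ran the trial.

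At stake is the Section II deliverable that study procedures be acceptable to clinic staff as well as patients, in preparation for the next trial. The ratings should describe providers who would have to live with the procedures without owning them. The randomised comparison and the patient-reported measures are not touched.

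**Working it through.** The plan has no calculation for the survey, so there is no figure to reproduce. The check is a comparison of the texts followed by an illustration of size.

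**1. Eligibility by group, as written**

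| Group | Aim 1 focus groups | Provider survey |
|---|---|---|
| Trauma chiefs (co-investigators) | Excluded | Not excluded |
| Research staff | Listed as eligible | Listed as eligible |
| Surgeon champions | Not excluded | Not excluded; send the links |
| Site PIs on the medical staff | Not excluded | Not excluded; send the links |

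One safeguard is lost between Aim 1 and the survey: the exclusion of chiefs. The other groups were not excluded in Aim 1 either. What changes for them is the task. Aim 1 was formative input before the trial, whereas the survey rates the trial after it has run.

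**2. How far study affiliation could move a pooled rating**

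Inputs:
- From the documents: at most n = 80 respondents at 4 sites, an average of 80/4 = 20 per site.
- Assumed: k = number of study-affiliated respondents, 4 to 20 (4/80 = 5% to 20/80 = 25%).
- Assumed: p = favourable share among independent providers, 0.60 to 0.80.
- Assumed: q = favourable share among affiliated respondents, from p to 1.00.

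Formula: observed share = [k·q + (n − k)·p]/n, so shift = k·(q − p)/n.

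Results with n = 80:

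| k | p | q | Observed | Shift (points) |
|---|---|---|---|---|
| any | any | = p | p | 0 |
| 4 | 0.80 | 0.90 | 0.805 | 0.5 |
| 4 | 0.70 | 1.00 | 0.715 | 1.5 |
| 8 | 0.70 | 1.00 | 0.730 | 3.0 |
| 16 | 0.70 | 1.00 | 0.760 | 6.0 |
| 20 | 0.60 | 1.00 | 0.700 | 10.0 |

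The last row in full: (20 × 1.00 + 60 × 0.60)/80 = 56/80 = 0.70.

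Chiefs alone, assuming one per site and all responding, give k = 4. Over the same grid their effect is at most 4 × (1.00 − 0.60)/80 = 0.02, or 2 points.

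Because 80 is a ceiling, the affiliated share could be larger. If half that number answered (80/2 = 40) and 8 were affiliated, then p = 0.70 and q = 1.00 would give a shift of 8 × 0.30/40 = 0.06 instead of 0.03.

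**3. Effect of separating the groups**

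Summarising only respondents with no study role returns the estimate from the mixture to p, whatever k and q are. The remedy therefore does not depend on knowing the size of the bias.

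**The case against.** The case on the other side is substantial.

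- **Bias is not shown.** A reader might infer that the ratings are in fact inflated. The documents do not support this: nothing says that any member of the study team will respond, or how they would rate. If affiliated staff are few or rate like others, the shift is near zero. This stands.
- **Co-investigators enter only by omission.** No text invites chiefs, site PIs or champions to respond, and describing the latter two as senders suggests that they may not be meant as respondents. This stands, but criteria should settle who is eligible, and these do not.
- **The Aim 1 contrast is narrow.** Aim 1 also listed research staff and excluded only the chief. It would be wrong to say that the plan removed a general bar on study personnel. The stated reason also concerns focus groups, where a chief's presence might influence what others say; a survey completed individually in REDCap lacks that route. The conflict of interest in rating one's own study remains.
- **Research staff is ambiguous.** It could mean trauma-center research personnel in general. However, inclusion criterion 4 for Aim 2 patients uses the term for this study's staff. A role item resolves the doubt.
- **No threshold exists to cross.** A reader might infer that a few points could carry a site past a benchmark. No provider benchmark, scoring rule or pass mark is given, and the items may be reported as mean scores.
- **The survey is secondary.** It is a descriptive addition after the intervention, absent from the Aim 2 analysis text. Treating its ratings as the trial's main outcomes would overstate the matter.
- **Safeguards exist.** Confidentiality, de-identification and entry in REDCap reduce pressure from the sender, so a change of sender is optional. They do nothing about affiliated respondents' own answers.
- **Study staff know the procedures.** Dropping all research staff would lose useful information. This stands, and it favours separate reporting over wholesale exclusion.

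**Conclusion.** The point holds as a risk. The provider survey leaves study-affiliated people eligible, drops without explanation the one exclusion that Aim 1 justified by bias, and provides no means of separating their ratings from those of ordinary providers. The direction of concern is upward.

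The size cannot be derived from the documents. The range of 0 to 10 percentage points rests entirely on assumed values (4 to 20 affiliated respondents of 80, independent endorsement of 0.60 to 0.80, affiliated endorsement from equal to 1.00), and zero is a credible value. Restoring the exclusion of chiefs alone would remove at most about 2 points under those assumptions, so most of the protection comes from recording study role.

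The consequence is limited to how far the survey can support the claim that staff accept the procedures. It is a modest weakness, worth correcting because the correction costs little and the protocol already accepts the principle.

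**What to change.** 1. Add an exclusion to the provider-survey criteria in Section III: trauma chiefs who are co-investigators, as in Aim 1.
2. Add one study-role item to the survey's demographic questionnaire: site PI, surgeon champion, co-investigator, research staff on this study, or none.
3. State in Section VI (Aim 2) that the main provider summary uses respondents with no study role, and that study-affiliated respondents are reported separately. Because a role within a site may identify a person, report the affiliated group pooled across sites.
4. Optional: send the REDCap link from the coordinating team, and report numbers invited and response rates by site.

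The cost is a short protocol amendment, one extra question and a few fewer respondents in the main summary. If the sender is changed, the response rate may fall slightly.
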